### 3.1 SCHEMATIC OF STUDY DESIGN

An overview of the study design is provided in Figure 1.

Figure 1 Overview of Study Design

### 4. STUDY DESIGN

#### 4.1 OVERALL DESIGN

An overview of the study design is provided in Section 3.1.

Each participant with ASD will be evaluated using several scales and tests at each visit at the clinic. A total of four clinic visits and two phone contacts are planned (screening period included; see Table 1). In addition, digital biomarker data will be collected from all participants. *Typically developing (TD)* healthy participants will be enrolled for validation of *digital* biomarkers only, see Table 2.

#### 4.1.1 Length of the Study

The total duration of the study (from screening through to study completion) for each participant will be approximately 15 weeks divided as follows:

- Screening and run-in period: up to 4 weeks. However, in case of unexpected delays due to logistical or technical reasons (e.g., sickness of caregivers or raters), the screening period may be extended to up to 6 weeks.
- Study period: 12 weeks.

#### 4.2 SCIENTIFIC RATIONALE FOR STUDY DESIGN

In contrast to an extensive literature on RRBs in subjects with ASD there are considerable gaps in the knowledge about the available and widely used scales (e.g., Repetitive Behavior Scale-Revised [RBS-R]) to assess these behaviors, particularly in clinical trials.

The overall study design with four planned clinic visits including a screening visit and a week 12 visit (see Section 1.2) aims to mimic the design of a drug interventional study over 12 weeks and will help to evaluate the performance of these scales under conditions comparable with interventional studies over 12 weeks. A second administration of all RRB scales 2 weeks after the Baseline visit was judged as

appropriate to assess test-re-test reliability. These visits are also appropriate to estimate internal consistency, stability, variability, minimal clinically important differences of included scales.

The study rationale is provided in Section 2.1.

### 4.2.1 Rationale for Study Population

Children, adolescents and adults (aged 5-45 years) with clinical diagnosis of ASD according to DSM-5 criteria and confirmed by Autism Diagnostic Observational Schedule (ADOS-2) will be enrolled. The lower age limit (5 years) will allow building a significant database from broad pediatric population. Although data suggest that the diagnosis of ASD is possible below the age of 5, the diagnosis is less reliable and may not be stable, and as a consequence will be excluded from this trials, although younger participants may be included in future trials.

Participants with at least moderate ASD symptoms and current presence of RRBs will be recruited to allow the monitoring of these behaviors during the study. To this aim, only participants with a Clinical Global Impression-severity (CGI-S)  $\geq$  4 (at least moderately-ill) and a Children's Yale-Brown Obsessive Compulsive Scale in Autism Spectrum Disorder (CY-BOCS-ASD) total score of at least 12 at screening will be enrolled. Participants with a low intelligence quotient (IQ) below 50 (Stanford-Binet Intelligence Scales 5th edition Abbreviated Battery Intelligence Quotient scale (ABIQ) will be excluded because of the higher prevalence of significant co-morbidities in this population.

Since there is wide consensus that the nature and intensity of RRBs depend on age and IQ, participants will be recruited into six cohorts of 15 participants to ensure enough variance across these two factors. Cohorts will be stratified firstly on ABIQ (participants who have an ABIQ  $\geq$  70 versus participants who have an ABIQ  $\geq$  50 and < 70), and secondly based on age (children, adolescents and adults; see Section 5).

## 4.2.2 Rationale for Control Group

This study includes a group of TD healthy male and female participants (15 children age 5 to 12 years, 15 adolescents age 13 to 17 years, and 15 adults age 18 to 45 years). The TD healthy participants will be needed to compare and validate the digital biomarkers versus participants with ASD. The TD healthy control group will participate in collection of digital biomarker data (see Schedule of Activities [SoA] for digital biomarkers, Table 2) and except of the Reading the Mind in the Eyes Test (RMET) needed as anchor data for the analysis of digital biomarkers, no clinical scales will be performed in the TD healthy control group since these scales are not suitable for typically developed individuals (see main SoA, Table 1).

### 4.2.3 Rationale for Biomarker Assessments

There are several limitations of the current clinical assessments performed during clinical visits including: (1) severity of a participant's symptoms may vary from day-to-day;

(2) the episodic nature of symptoms mean that the symptom may not occur during the clinical visit; (3) effects can be masked at clinic visits by a variety of factors, including the "White-Coat Effect" where participants try harder at performance outcome measures when a doctor is present; (4) the subjectivity of participant or caregiver evaluation of symptom severity; and (5) the assessments are done in a non-naturalistic environment.

Digital biomarkers have the potential to address these issues by providing frequent and objective measurements in the participant's normal environment. Digital biomarkers are defined here as physiological and behavioral data collected with consumer electronics for the purpose of tracking health-related outcomes. A digital biomarker approach has been developed for this study where participants will be tracked with a combination of: (1) daily participant and caregiver-reported outcome measures ('surveys'), (2) daily performance outcome measures ('active tests') and (3) continuous passive monitoring of participant behavior.

A dedicated smartphone and wearable device will be provided to each participant and caregiver. The active tests and surveys contained in the smartphone app will provide regular daily recording of disease signs, enabling the characterization of progression over time. Analysis of the data will aim to identify the occurrence of repetitive movements, understand patterns of movement around the home and beyond, the stereotype of sensor signals across days as a proxy for ritualistic behavior, changes in heart rate associated with anxiety, and aspects of social functioning. This data will provide continuous objective quantification of these variables throughout the study.

#### 4.3 END OF STUDY DEFINITION

The end of the study is defined as the date when the last participant last observation (LPLO) occurs. LPLO is expected to occur approximately 12 weeks after the last participant had his/her Baseline visit.

#### 5. STUDY POPULATION

The study population rationale is provided in Section 4.2.1.

The participants are children age 5 to 12 years, adolescents age 13 to 17 years, and adults age 18 to 45 years who meet all diagnostic criteria of ASD according to the DSM-5 criteria (see Section 5.1).

Approximately 90 participants with ASD will be enrolled into six cohorts with approximately 15 participants each by two factors ABIQ and age:

- ABIQ: participants with ABIQ  $\geq$  70 vs participants with (ABIQ  $\geq$  50 and < 70)
- Age: children 5 to 12 years; adolescents 13 to 17 years and adults 18 to 45 years

In addition, 45 TD healthy participants (15 children age 5 to 12 years, 15 adolescents age 13 to 17 years, and 15 adults age 18 to 45 years) will be enrolled for validation of digital biomarkers only. See Section 9.1 (sample size justification) for further details.

Prospective approval of protocol deviations from recruitment and enrollment criteria, also known as protocol waivers or exemptions, is not permitted.

#### 5.1 INCLUSION CRITERIA

Participants with ASD and TD healthy participants are eligible to be included in the study only if all of the following criteria apply:

# Inclusion criteria specific to typically developing healthy participants:

1. Male and female TD healthy participants age 5 to 45 years inclusive.

# Inclusion criteria specific to typically developing healthy participants and participants with ASD:

- Able and willing to provide written informed consent or assent, as per local requirements according to International Council for Harmonisation (ICH) and local regulations. Alternatively, a legally authorized representative must be able to consent for the participant according to ICH and local regulations and assent must be given whenever possible.
- 3. Availability of a parent or other reliable caregiver who is fluent in English and has frequent and sufficient contact with the participant (see Section 8.1.1.1). The same person must agree to accompany the participant to all clinic visits and provide information about the participant's behavior and symptoms and must agree to oversee the participant's adherence with protocol-specified procedures.
- In the Investigator's opinion, the participant must be able to participate and is deemed appropriate for participation in the study, capable of following the study schedule of assessments.
- 5. English proficiency compatible with the study measurements as judged by the Investigator.
- 6. Hearing, vision, *and speech* compatible with the study measurements as judged by the Investigator.

# Inclusion criteria specific to participants with ASD:

- 7. Male and female participants with ASD 5 to 45 years inclusive.
- Abbreviated Intelligence Battery Quotient (ABIQ) ≥ 50 as assessed by Stanford-Binet Intelligence Scales fifth Edition (SB5) at screening or within the last 12 months prior to screening.
- 9. ASD diagnosis by DSM-5 criteria by a qualified clinician.
- The ASD diagnosis confirmed by ADOS-2 done by a certified rater at screening or within the last 6 months prior to screening.

- Children's Yale-Brown Obsessive Compulsive Scale modified for ASD (CY-BOCS-ASD) total score of at least 12.
- Clinical Global Impression–Severity (CGI-S) scale ≥ 4 (moderately ill) at screening about participant's current autism severity (see Section 8.1.1.7).
- 13. Medications should be stable for 4 weeks (6 weeks for Fluoxetine) and behavioral interventions for 6 weeks prior to screening. Investigator expects stability of these treatments for the duration of the study.

#### 5.2 EXCLUSION CRITERIA

Participants with ASD and TD healthy participants are excluded from the study if any of the following criteria apply:

# **Exclusion criteria specific to** *typically developing* **healthy participants**:

1. Typically developing healthy participants with first degree relative with ASD.

# Exclusion criteria specific to typically developing healthy participants and participants with ASD:

- Participation in an investigational drug or device study within 4 weeks, or five times
  the half-life (if it is a drug study) of the investigational molecule (whichever is longer),
  prior to screening and the participant is expected not to enroll in any other trial
  during the study.
- Co-occurring disease or condition that could interfere with, or treatment which might interfere with, the conduct of the study, or that would, in the opinion of the Investigator, pose an unacceptable risk to the participant in this study.
- Unstable or uncontrolled clinically significant psychiatric and/ or neurological disorder that may interfere with the objectives of the study.

#### Exclusion criteria specific to participants with ASD:

- 5. Participants with known "syndromic" ASD (e.g., Fragile-X syndrome, Angelman Syndrome, Prader-Willi, Rett's syndrome, tuberous sclerosis, Dup15q syndrome).
- 6. History of alcohol misuse and/ or illicit drug use during the last 12 months *prior to screening*.

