#### 8.5 TIMING OF STUDY ASSESSMENTS

# 8.5.1 Screening Assessments

Written informed consent for participation in the study must be obtained before performing any study-specific screening tests or evaluations. Informed Consent Forms (ICFs) and assent forms for enrolled participant and for participants who are not subsequently enrolled will be maintained at the study site.

All screening assessments must be completed and reviewed to confirm that participants meet all eligibility criteria. The Investigator will maintain a screening log to record details of all participants screened and to confirm eligibility or record reasons for screening failure

An Eligibility Screening Form (ESF) documenting the Investigator's assessment of each screened participant with regard to the protocol's inclusion and exclusion criteria is to be completed by the Investigator and kept at the investigational site.

Screening assessments will be performed during the time window indicated in the SoA (see Section 1.2), i.e., within 4 to 2 weeks before the Baseline visit. However, in case of unexpected delays due to logistical or technical reasons (e.g., sickness of caregivers or raters), the screening period may be extended to up to 6 weeks.

At screening, tests for illicit drugs and alcohol misuse are at the Investigator's discretion. The Investigator will decide if any tests are required or not to confirm eligibility in context of exclusion criterion #6. In addition, the selection of the appropriate tests and test parameters and the appropriate communication of possible findings to participant and parents according to local regulations will be at the discretion of the Investigator. Roche will support sites in the implementation process should the sites need (e.g., provision of urine dipsticks).

Note: Any positive tests for amphetamines will need to be reviewed carefully by the Investigator on a case by case basis, because a significant proportion of people with ASD are taking stimulants such as methylphenidate for their attention-deficit problems. In such a case of a misleading drug alert, a possible study participant will not be excluded from the study.

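### The alcohol and drug exclusion applies only to participants with ASD, although 30 of the 45 typically developing controls are now adolescents or adults

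*Combined protocol and SAP*

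**What the plan says.** Section 5.2 sorts the exclusions under three headings.

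- **TD only:** a single criterion, "Typically developing healthy participants with first degree relative with ASD".
- **Both groups:** criteria 2 to 4. Criterion 3 covers "Co-occurring disease or condition that could interfere with, or treatment which might interfere with, the conduct of the study", or an unacceptable risk in the investigator's opinion. Criterion 4 covers "Unstable or uncontrolled clinically significant psychiatric and/ or neurological disorder that may interfere with the objectives of the study". Neither names alcohol or drugs.
- **ASD only:** under "Exclusion criteria specific to participants with ASD" stand syndromic ASD (criterion 5) and "History of alcohol misuse and/ or illicit drug use during the last 12 months" before screening (criterion 6).

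The synopsis has the same arrangement. Section 5.1 admits "Male and female TD healthy participants age 5 to 45 years inclusive", and Section 9.1 sets 15 TD children, 15 TD adolescents and 15 TD adults. According to the amendment's summary of changes, the TD upper age limit was previously 12. The same amendment added the reference to screening in criterion 6 and left the criterion under the ASD heading.

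On testing, Section 8.5.1 says "The Investigator will decide if any tests are required or not to confirm eligibility in context of exclusion criterion #6". Section 8.2.1 places alcohol and drug use within medical history. Medical History is a row of Table 1, which is for ASD participants only. Table 2, which governs TD participants, has no such row.

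Section 4.2.2 gives the purpose of the controls: "The TD healthy participants will be needed to compare and validate the digital biomarkers versus participants with ASD". Section 9.2.5 plans to explore that difference.

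**The concern.** With controls aged 5 to 12, an ASD-only alcohol and drug criterion had little practical effect. With adolescents and adults up to 45 among the controls, it becomes a difference in how the two groups are selected. An adult with ASD and illicit drug use in the past year must be excluded; a TD adult with the same history meets no named exclusion.

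The controls are enrolled for one contrast, digital biomarkers in ASD versus TD. The measures include spatial working memory, emotion recognition, speech, movement and possibly heart rate, all of which alcohol or drug use could plausibly affect. If the history is not recorded in controls, the analyst can neither describe the imbalance nor adjust for it nor run a sensitivity analysis without those participants.

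**Working it through.** **1. Does the asymmetry exist in the current text?** Yes. The criterion appears under the ASD heading in Section 5.2 and in the synopsis, and under no other heading. Section 5.3 sets no lifestyle restrictions. Section 6.2 generally bars concomitant therapies in TD participants, but that concerns treatments, not alcohol or illicit drugs.

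**2. Does screening or data collection close the gap?** Not explicitly. Section 8.5.1 links the decision on testing to criterion 6, which does not apply to controls. Section 8.2.1 is not worded as ASD-only, but the schedule that would implement it for controls (Table 2) lacks the row.

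**3. How many controls are concerned?** The plan's counts reproduce: 3 × 15 = 45 TD and 6 × 15 = 90 ASD. Adolescents and adults make up 15 + 15 = 30 of 45 controls (67%) and 4 × 15 = 60 of 90 ASD participants.

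**4. How large could the effect be?** The documents give no prevalence and no effect of substance use on any biomarker, so both are assumptions here. Let *p* be the share of the 30 older controls with such a history, and *d* the difference between them and other controls in SD units. Take the ASD share as zero, which is the largest contrast for a given *p*.

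- Expected number = 30 × *p*
- Chance of at least one = 1 − (1 − *p*)^30
- Shift in the mean of the older controls = *p* × *d*

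| Assumed *p* | Expected number | Chance of at least one | Shift, *d* = 0.5 SD | Shift, *d* = 1.0 SD |
|---|---|---|---|---|
| 2% | 0.6 | 0.455 | 0.01 | 0.02 |
| 5% | 1.5 | 0.785 | 0.025 | 0.05 |
| 10% | 3 | 0.958 | 0.05 | 0.10 |
| 20% | 6 | 0.999 | 0.10 | 0.20 |
| 30% | 9 | >0.999 | 0.15 | 0.30 |

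**5. Compare with sampling error**, with unit SD in both groups.

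- Adolescents and adults pooled, 30 TD v 60 ASD: √(1/30 + 1/60) = 0.224 SD
- One age band, 15 TD v 30 ASD: √(1/15 + 1/30) = 0.316 SD

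At *d* = 0.5 SD the largest shift is 0.15/0.224 = 0.67 of a standard error pooled and 0.15/0.316 = 0.47 in one band. Only the most extreme combination (30% and 1.0 SD) exceeds one standard error, and only in the pooled contrast: 0.30/0.224 = 1.34. In one band it is 0.30/0.316 = 0.95.

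**The case against.** Four counter-arguments carry weight.

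- **Investigator judgement.** Shared exclusion 3 could reach alcohol or drug misuse, and shared inclusion 4 requires every participant to be suitable in the investigator's opinion. No site is obliged to enrol such a control. This stands, but it leaves the outcome to each site, whereas for ASD participants the bar is explicit.
- **Testing is discretionary in ASD too.** A reader might infer that substance-using controls will be compared with ASD participants shown to be free of use. The documents do not support that. The asymmetry lies in the rule; it does not guarantee zero use in the ASD group.
- **The data gap is not certain.** Section 9.2.5 defers detail to a technical document that is not part of the material. The rules on pre-existing conditions (Appendix 1, Section 2.1.3; Appendix 3, Section 5) would probably record a diagnosed use disorder. They would not record use short of a diagnosis, and Table 2 still schedules no such history.
- **The groups already differ by design.** ASD participants may continue stable medication while controls generally take none, so aligning criterion 6 will not make the groups alike in exposure to centrally acting substances. That is true, but it is no reason to keep a further difference that is easily removed.

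One might also argue that the sponsor chose the ASD-only placement, since Version 2 edited the criterion and kept its heading. A reader might equally infer an oversight. The documents state no reason, so neither reading is established.

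**Conclusion.** The eligibility difference is real and avoidable: a 12-month alcohol and drug exclusion binds the ASD group and not the controls, 30 of whom are aged 13 to 45, and the corresponding history is not scheduled for controls. It touches only the exploratory ASD-versus-TD comparison of digital biomarkers. The primary and secondary objectives rest on clinical scales in ASD participants and are unaffected.

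Its size cannot be derived from the documents. Over the assumed range (2% to 30% of older controls, 0.5 to 1.0 SD) the shift runs from 0.01 to 0.30 SD, and it stays below one standard error in every case but one. It is probably small relative to sampling error.

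A reader might go further and conclude that the gap pulls controls towards the ASD group and hides a true difference. The documents do not support this: they say nothing on how substance use moves any of these measures, and the direction could differ from one measure to another. This is a worthwhile, inexpensive improvement; it does not invalidate the comparison.

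**What to change.** 1. In Section 5.2 and the synopsis, list the alcohol and drug criterion under the exclusions common to TD and ASD participants.
2. Check the numbering. If the criterion follows shared exclusion 4 and the list is renumbered, it becomes number 5 and syndromic ASD becomes number 6, so the reference to criterion 6 in Section 8.5.1 would point to the wrong item. Update that reference.
3. Add the alcohol and drug history item of Section 8.2.1 to Table 2, so that it is recorded for controls. Step 1 alone does not do this.

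If the sponsor has a reason for the ASD-only rule, the protocol should state it; step 3 is still needed so that the imbalance can be described and examined.

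The cost is a short amendment, a few more screen failures among adolescent and adult controls, and one more history item at screening. Sample size and the planned analyses do not change.

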#### 5.3 LIFESTYLE CONSIDERATIONS

No lifestyle restrictions required.

#### 5.4 SCREEN FAILURES

Screen failures are defined as participants who consent to participate in the clinical study but are not subsequently enrolled in the study.

The Investigator will maintain a screening log to record details of all participants screened and to confirm eligibility or record reasons for screening failure.

Screen-failed participants can be re-screened with Sponsor permission (Medical Monitor or designee) if there is a substantial change in the participant's general condition (e.g., a new medication should have been stable for at least 4 weeks at re-screening) and if recruitment for the study is still ongoing. Re-screening of participants with ASD will not be allowed if the participant failed earlier to meet the disease-specific inclusion criteria (CYBOCS-ASD, ADOS-2, CGI-S, and ABIQ).

Screening assessments will be performed during the time window indicated in the SoA (see Section 1.2), i.e., within 4 to 2 weeks before the Baseline visit. However, in case of unexpected delays due to logistical or technical reasons (e.g., sickness of caregivers or raters), the screening period may be extended to up to 6 weeks. Beyond 6 weeks the participant is considered a screen failure, but can be re-screened.

# 5.5 RECRUITMENT PROCEDURES (TYPICALLY DEVELOPING HEALTHY PARTICIPANTS)

Participants will be identified for potential recruitment using pre-screening enrollment logs, clinical database and IEC/IRB approved advertisements prior to consenting to take place on this study.

